6.2.3. Treatment Period (Day 1 to Day 21)

6.2.3.1. Day 1

For Cycle 1, if baseline visit activities occur within 1 day prior to Day 1, the following assessments do not need to be repeated. For Cycle 2 and beyond, these assessments have a window of -2 days:

- Physical examination (see Section 7.5.4)
- Weight
- ECOG performance status (see Appendix F)
- Serum chemistry panel (detailed in Section 7.5.3) to be evaluated prior to infusion.
 Hold dose if blood glucose level is >250 mg/dL.
- CBC with differential (detailed in Section 7.5.3) to be evaluated prior to infusion.
- Pregnancy test (for patients of childbearing potential; performed locally; does not need to be repeated if performed within 3 days of Day 1)
- Thyroid function tests (detailed in Section 7.5.3; to include TSH, T3 or free T3, and free T4). Day 1 of each odd-numbered cycle only (i.e. Cycles 1, 3, 5, 7, etc.)

The following procedures must be performed on Day 1 of every cycle:

- Vital signs (within 60 minutes prior to LV infusion, within 60 minutes prior to pembrolizumab infusion, within 2 hours of ending each infusion, and during infusion/s as clinically indicated (See Section 7.5.2)
- Predose blood samples for biomarkers (Cycle 1 only). See time points in Appendix E.
- Predose blood samples for PK (Cycle 1 only). See time points in Appendix B.
- Post dose blood samples for PK (Cycle 1 only). See time points in Appendix B.
- Predose blood samples for ATA (Cycle 1 only). See time points in Appendix B.
- LV infusion (if dosing criteria in Section 5.2.3.5 are met)
- Pembrolizumab infusion
- Collection of concomitant medication information
- Collection of AEs

6.2.3.2. Day 3 (Part B Cycle 1 required for patients in US sites, optional for patients outside US sites; window: Days 3-4)

Blood samples for PK

6.2.3.3. Day 5 (Part A Cycle 1 only; window: Days 4-7)

Fresh tumor biopsy

- Blood samples for PK
- Blood samples for biomarkers
- Collection of concomitant medication information
- Collection of AEs

6.2.3.4. Day 8 (Cycles 1-2 only; ±2 days)

- CBC with differential (detailed in Section 7.5.3)
- Serum chemistry panel (detailed in Section 7.5.3)
- Collection of concomitant medication information
- Collection of AEs
- Cycle 1 only:
 - Blood samples for PK

6.2.3.5. Day 15 (Cycle 1 only; ±2 days)

- Fresh tumor biopsy only for patients enrolled in Part B (window: Days 15–21)
- Blood samples for PK
- Collection of concomitant medication information
- Collection of AEs

6.3. Parts C (q1wk LV dosing) and D (Days 1 and 8 LV dosing)

6.3.1. Screening Visit (Day -28 to 1)

- Informed consent
- Study eligibility per inclusion/exclusion criteria
- Medical history (See Section 7.1)
- Brain CT or MRI
- Biopsy, archival or freshly obtained, submitted for the following:
 - Central assessment of exploratory biomarker assessments (see Appendix E)
 - Part D only: Local laboratory determination of PD-L1 CPS <10 by a PD-L1 IHC assay using the 22C3 clone (see Section 7.1)
- ECG (see Section 7.1.1)
- Serology for hepatitis B surface antigen and antihepatitis B core antibody (detailed in Section 7.5.3)
- PCR for hepatitis C virus (detailed in Section 7.5.3)
- HbA1c and fasting blood glucose (detailed in Section 7.5.3)
 - If HbA1c or fasting glucose is elevated with confirmation upon repeat testing (HbA1c ≥6.5%, fasting glucose ≥126 mg/dL, or ≥7.0 mmol/L), the patient should receive glucose management before Cycle 1 Day 1 or within the first week of Cycle 1
- PT/PTT/aPTT/INR (detailed in Section 7.5.3)
- CT of chest, abdomen, and pelvis (and neck if clinically indicated) (MRI may also be acceptable; see Section 7.1)

- Thyroid function tests (detailed in Section 7.5.3)
- Collection of concomitant medication information
- Collection of AEs

6.3.2. Baseline Visit (Day -7 to 1)

- Height and weight (see Section 7.1)
- Vital signs (see Section 7.5.2)
- Physical examination (see Section 7.5.4)
- ECOG Performance status (see Appendix F)
- Serum chemistry panel (detailed in Section 7.5.3)
- CBC with differential (detailed in Section 7.5.3)
- Pregnancy test for patients of childbearing potential performed within 3 days prior to Cycle 1 Day 1 (performed locally)
- Collection of concomitant medication information
- Collection of AEs

6.3.3. Treatment Period (Day 1 to 21 of each cycle)

6.3.3.1. Day 1

The following assessments have a window of -2 days. If baseline visit activities occur within 2 days prior to Day 1, the assessments do not need to be repeated.

- Pre-dose
 - Physical exam
 - Weight
 - ECOG performance status (see Appendix F)
 - Serum chemistry panel (detailed in Section 7.5.3) to be evaluated prior to infusion.
 Hold dose if blood glucose level is >250 mg/dL.
 - CBC with differential (detailed in Section 7.5.3) to be evaluated prior to infusion.
 - Pregnancy test (for patients of childbearing potential; performed locally; does not need to be repeated if performed within 3 days of Day 1)
 - Thyroid function tests (detailed in Section 7.5.3; to include TSH, T3 or free T3, and free T4). Day 1 of each odd-numbered cycle only (i.e. Cycles 1, 3, 5, 7, etc.)

The following procedures must be performed on Day 1:

- Vital signs (within 60 minutes prior to LV infusion, within 60 minutes prior to pembrolizumab infusion, within 2 hours of ending each infusion, and during infusion/s as clinically indicated (See Section 7.5.2)
- Predose blood samples for biomarkers (Cycle 1 only). See time points in Appendix D.
- Predose blood samples for PK (Cycle 1 only). See time points in Appendix D.
- Post dose blood samples for PK (Cycle 1 only). See time points in Appendix D.
- Predose blood samples for ATA (Cycle 1 only). See time points in Appendix D.
- LV infusion (if dosing criteria in Section 5.2.3.5 are met)
- Pembrolizumab infusion
- Collection of concomitant medication information
- Collection of AEs

6.3.3.2. Day 3 (Cycle 1 only; required for patients in US sites, optional for patients outside US sites; window: Days 3-4)

Blood samples for PK

6.3.3.3. Day 8

- Pre-dose
 - Serum chemistry panel (detailed in Section 7.5.3) to be evaluated prior to infusion (Cycles 1 and 2 only).
 - CBC with differential (-2-day window; detailed in Section 7.5.3) to be evaluated prior to infusion.
 - Blood samples for PK assessment (Cycle 1 only; see Appendix D)
- Vital signs (within 60 minutes prior to LV infusion, within 2 hours of ending of infusion, and during infusion as clinically indicated. See Section 7.5.2)
- LV infusion
- Post-dose
 - Cycle 1 only: blood samples for PK assessment (Appendix D)

6.3.3.4. Day 15

Part C

- Pre-dose
 - Serum chemistry panel (detailed in Section 7.5.3) to be evaluated prior to infusion (Cycles 1 and 2 only).
 - CBC with differential (-2-day window; detailed in Section 7.5.3) to be evaluated prior to infusion.
 - Blood samples for PK assessment (Cycle 1 only; see Appendix D)
- Vital signs (within 60 minutes prior to LV infusion, within 2 hours of ending of infusion, and during infusion as clinically indicated. See Section 7.5.2)
- LV infusion (if dosing criteria in Section 5.2.3.5 are met)

- Post-dose
 - Cycle 1 only: blood samples for PK assessment (Appendix D)

Part D

CBC with differential (-2-day window; detailed in Section 7.5.3 (Cycles 1 and 2 only).

6.4. Response Assessments

Time points for radiographic exams should be calendar based and do not depend on cycle visits (see Section 7.2). Imaging should be conducted on the following schedule until disease progression, unacceptable toxicity, start of a new cancer therapy, consent withdrawal, investigator decision, study termination by the sponsor, or death, whichever comes first:

Every 6 weeks (±3 days) for 12 months after the first dose of LV and pembrolizumab

Every 12 weeks (±7 days) thereafter

No additional scans or response assessments are required after the safety follow-up period, however additional scans or response assessments may be performed as part of the patient's standard of care at any time.

6.5. End of Treatment Visit (30 to 37 days after last dose of study drug)

End of treatment (EOT) visits should occur 30 to 37 days after the last dose of study drug unless delayed due to an AE. Note: The time to EOT visit may be longer than 37 days, but in no case should it be <30 days. However, EOT evaluations must be performed before initiation of a new therapy. If EOT evaluations are completed before 30 days after the last study treatment, the patient will be contacted 30 to 37 days following the last treatment to assess for AEs.

- ECOG Performance status (see Appendix F)
- Physical examination (see Section 7.5.4)
- Pregnancy test (for patients of childbearing potential; performed locally)
- Serum chemistry panel (detailed in Section 7.5.3)
- CBC with differential (detailed in Section 7.5.3)
- HbA1c (performed locally)
- CT of chest, abdomen, and pelvis (and neck if clinically indicated) (MRI may also be acceptable; see Section 7.1) (not required if conducted within 4 weeks prior to EOT)
- Collection of concomitant medication information
- Collection of AEs

If patients are discontinuing treatment due to PD, and a biopsy was done as standard of care at disease progression, a tumor sample is requested, if available.

6.6. Follow-up

Patients who discontinue study treatment in the absence of disease progression will remain on the study for follow-up until withdrawal of consent, initiation of a new anticancer therapy, death, or study closure, whichever occurs first. The first follow-up visit will occur 6 weeks (±1 week) from the most recent prior radiographic response evaluation. Subsequent follow-up visits will be scheduled for 6 weeks (±1 week) from the previous follow-up visit. After 1 year on study, the frequency of follow-up visits will be reduced to every 12 weeks (±1 week).

The following assessments will be conducted at follow-up visits until progression or initiation of a new anticancer treatment through the end of the safety follow-up period:

- Physical examination (see Section 7.5.4)
- CT of chest, abdomen, and pelvis (and neck if clinically indicated) (MRI may also be
 acceptable; see Section 7.1); after a year of follow-up, reduce frequency to institution's
 standard of care until progression or initiation of a new anticancer therapy.
- Concomitant medication information and AEs to be collected if serious and considered to be study treatment-related.

Safety Follow-Up

Patients discontinuing treatment will be followed for the protocol required safety follow-up period, unless additional safety concerns warrant further follow-up:

- 30 days post treatment for LV and
- 90 days post treatment for pembrolizumab.

No additional follow-up is required after the safety follow-up period.

After disease progression or initiation of a new anticancer treatment, survival follow-up will be conducted, every 12 weeks (±2 weeks) starting from the last radiographic scan demonstrating disease progression or from initiation of the new anticancer treatment until completion of the safety follow-up period, death, or study closure, whichever comes first. Follow-up may be conducted with clinic visits or telephone calls. No further response assessments will be conducted.

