7.5.1.3. Reporting Periods for Adverse Events and Serious Adverse Events

The safety reporting period for AEs is from study Day 1 (predose) through the EOT visit or 30 days after the last study treatment, whichever is later. The reporting period for SAEs is from study Day 1 (predose) through the EOT visit or 90 days after the last study treatment, whichever is later. Events will be recorded at each examination on the Adverse Event CRFs/worksheets. However, all study protocol-related AEs are to be recorded from the time of informed consent. All SAEs that occur after the safety reporting period and are considered study treatment-related in the opinion of the investigator should also be reported to the sponsor. The investigator will make every attempt to follow all patients with non-serious AEs for outcome.

The reporting timeframe for AEs meeting any serious criteria is described in Section 7.5.1.4.

SAEs will be followed until significant changes return to baseline, the event stabilizes (recovering/resolving) or is no longer considered clinically significant by the investigator, or the patient dies or withdraws consent. All non-serious AEs will be followed through the safety reporting period. Certain non-serious AEs of interest may be followed until resolution, return to baseline, or study closure, whichever comes first. In particular these include AEs of peripheral neuropathy in all patients.

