- I Blood glucose sample should be obtained before administration of study drugs or any glucose-containing fluid. Hold dose if blood glucose level is >250 mg/dL or >13.9 mmol/L, testing may be repeated on same day of dosing. If HbAlc or fasting glucose are elevated (HbAlc ≥6.5%, fasting glucose ≥126 mg/dL or ≥7.0 mmol/L) upon repeat testing, patient should receive glucose management prior to or within one week of starting study treatment.
- J Thyroid function tests include TSH, T3 or free T3, and free T4.
- K To be collected if serious and considered to be study treatment-related.
- L For patients who discontinue study treatment, perform every 6 weeks (±1 week) during the first year, then reduce frequency per institution's standard of care until progression or initiation of a new anticancer therapy unless otherwise stated.
- M For patients receiving >200 mg LV per infusion (weight >80 kg), prophylactic G-CSF administration is required and will be given to patients on the day after study treatment is given, with a visit window of Day 2-4. If pegfilgrastim is used, a one-time dose is recommended. If daily growth factor support is used, treat for at least 5-7 days or until the absolute neutrophil count is >1000/mm³ (< Grade 2). Hold dose if dosing criteria outlined in Section 5.2.3.5 are not met.
- N Timing of response assessments should be calculated from Cycle 1 Day 1.
- O Refer to the laboratory manual for information on collection, processing, storage, and shipment of sample.
- P Not required if conducted within 4 weeks prior to EOT.
- O Cycles 1-2 only
- R For Cycle 2 and beyond, may be performed up to 2 days prior to Day 1.
- S For Part A and Part B Cohort 1, laboratory assessments are to be performed locally and centrally. For Part B Cohort 2, laboratory assessments are to be performed locally and results are to be submitted to the central laboratory (with the exception of pregnancy testing); detailed in Section 7.5.3.
- T Follow-up will occur every 6 weeks (±1 weeks) 30 days post last treatment for patients on LV only and 90 days for those on pembrolizamab.

Page 106 of 152

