APPENDIX C: SCHEDULE OF EVENTS (PARTS C AND D)

						21-day Cycle			
		Baseline/S	creening	Enrollment	Dl	D8	D15	EOT	Follow-up
Visit Window	,	D-28 to 1	D-7 to 1	D-7 to 1	See footnotes for window	See footnotes for window	See footnotes for window	30-37 days post last dose	Every 6 weeks ±1 week ^{B,V}
Informed consent		X	2 / 101	2 / 10 1	***************************************	***************************************	TI ALLEGO III	and about	and treat
	Inclusion/exclusion	X		1					
	Medical history	X		1					
	Physical Exam		X	1	XAQ			X	X
	Height (baseline only) and Weight		X	1	X ^{A,Q}				
	Vital signs ^C		X	d to	X	X	X^U		
	Brain CT or MRI	X		흹					
	Initiate collection of archived tumor specimen (if available) ^{N,V}	x		Eligibility documentation submitted to sponsor prior to study start					
	Freshly obtained biopsy ^{D,M,T} (see also Appendix E)	x		nentati					
	ECG	X		8 2					
Safety	Pregnancy test (performed locally) (patients of childbearing potential only)		XE	ity do	XE			X	
Assessments	ECOG performance status		X	漫图	$X^{A,P}$			X	
1	Hepatitis B and C screening ^Q	X		.					
1	CBC with differential ^{M,Q}		X	-	X _{AQ}	X	X_{Ω}	X	
1	PT/PTT/aPTT/INRQ	X							
	HbAlc ^{G,Q}	X						X	
	Fasting blood glucose ^{F,Q}	X		1					
	Serum chemistry panel ^{M,Q}		X		XAGQ	$X^{G,R}$	$X^{GR,S}$	X	
	Thyroid function tests ^{H,Q}	x			(e.g.,	ch odd-numbered cycle w Day 1 of Cycles 1, 3, 5,	7, etc)		
	Concomitant medications & AEs	study protoc	lect any related procedure in from the tri- termination	s that result in al or study	Collect from Day 1 (pr	redose) through 30 days (through EOT visit, wh	(AEs) or 90 days (SAEs) ichever is later ^{BI}	post last dose or	Χ'n
Treatment ^K	LV ^{KO,P}				X	X	X ^s		
Treatment.	Pembrolizumab				X				
	Samples for PK							_	
PK/ATA	Samples for ATA				Cycle 1 Only: See	e PK/ATA/Biomarker Ta	ibles (Appendix D and A	ppendix E)	
	Blood sample for biomarker analysis								
Response	CT or MRI of chest, abdomen, pelvis (and neck if clinically indicated) ⁵	x			Assessments to be performed every 6 weeks (±3 days) for the first 12 months and every 12 weeks (±7 days) thereafter, regardless of dose delays (see Section 7.2)			Χ ^N	X_1
	Subsequent anticancer therapy status (may be conducted with in-clinic visit or via phone calls)								х

Survival status (may be conducted with in-				v
clinic visit or via phone calls)				^

- A For Cycle 1 only, if baseline visit activities occur within 2 days prior to Day 1, these assessments do not need to be repeated.

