- O At least 7 days must elapse between administrations of LV. Hold dose if dosing criteria outline in Section 5.2.3.5 are not met.
- P For Cycle 2 and beyond, may be performed up to 2 days prior to Day 1.
- Q Laboratory assessments are to be performed locally and results are to be submitted to the central laboratory (with the exception of pregnancy testing); detailed in Section 7.5.3.
- R Cycles 1 and 2 only.
- S Part C only.
- T In Part D only, archival or freshly obtained tumor tissue will be used to determine eligibility based on PD-L1 CPS<10 status as determined locally by a PD-L1 IHC assay using the 22C3 clone.
- U Cycles 1 and 2 only for Part D and every cycle for Part C.
- V Follow-up will occur every 6 weeks (±1 weeks) 30 days post last treatment for patients on LV only and 90 days for those on pembrolizumab.

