#### 6.7.1 Adverse Events

Adverse events will be summarized by MedDRA Preferred Term in descending frequency of occurrence unless otherwise specified. For incidence reporting, if a patient reports more than one AE that was coded to the same system organ class or preferred term, the patient will be counted only once for that specific system organ class or preferred term.

A treatment-emergent AE(TEAE) is defined as a newly occurring or worsening AE after the first dose of study drug, through EOT visit or 30 days after last dose date whichever is later or through EOT visit or 90 days after last dose date for SAE. See Appendix C for details

Study SGNLVA-002 Ladiratuzumab vedotin Statistical Analysis Plan Seagen, Inc. - Confidential 01-May-2024 Page 19 of 32 regarding treatment-emergent classification. An overall summary of AEs will be provided. Summaries of AEs will be provided for the following, by preferred term, if not specified otherwise:

- All treatment-emergent AEs
- Treatment-emergent AEs related to SGN-LIV1A
- Treatment-emergent AEs related to both SGN-LIV1A and Pembro
- Treatment-emergent Serious Adverse Events (SAEs)
- Treatment-emergent SAEs related to SGN-LIV1A
- Treatment-emergent SAEs related to both SGN-LIV1A and Pembro
- Treatment-emergent AEs leading to dose delay of SGN-LIV1A
- Treatment-emergent AEs leading to dose reduction of SGN-LIV1A
- Treatment-emergent AEs leading to treatment discontinuation
- Treatment-emergent AEs leading to death
- Infusion-related reactions by preferred term
- DLTs
- Treatment-emergent AEs by system organ class, preferred term and maximum severity.
- Grade 3–5 treatment-emergent AEs
- Treatment-emergent AEs by system organ class and preferred term

All adverse events, adverse events leading to treatment discontinuation, and adverse events leading to death will be listed.

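### Follow-up visits collect only serious, treatment-related AEs, yet they fall inside the 90-day window for all SAEs; for LV-only patients, follow-up ends at Day 30 of that window

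*Protocol*

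**What the plan says.** **Follow-up visits.** Section 6.6 lists the assessments for follow-up visits, which last until progression or new anticancer therapy and run through the end of the safety follow-up period. The AE item reads: "Concomitant medication information and AEs to be collected if serious and considered to be study treatment-related". The schedules carry the same limit for the follow-up column: "To be collected if serious and considered to be study treatment-related" (Appendix A, footnote K; Appendix C, footnote I, in the same words).

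**SAE window.** Section 7.5.1.3 states: "The reporting period for SAEs is from study Day 1 (predose) through the EOT visit or 90 days after the last study treatment", taking the later of the two. The relatedness condition comes only after that: "All SAEs that occur after the safety reporting period and are considered study treatment-related in the opinion of the investigator should also be reported". Section 7.5.1.4 requires SAE reports within 24 hours whatever the relationship. SAP 6.7.1 counts treatment-emergent SAEs "through EOT visit or 90 days after last dose date for SAE", with no relatedness condition.

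**End of follow-up.** Section 6.6 sets safety follow-up at 30 days after LV and 90 days after pembrolizumab, and requires nothing further. Appendix C footnote V (and footnote T in Appendix A) gives "30 days post last treatment for patients on LV only and 90 days for those on pembrolizumab". Section 4.4.2 lists completion of safety follow-up as a reason to leave the study.

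**The concern.** A related-only rule makes sense after the all-cause SAE window has closed, and 7.5.1.3 uses it there. Under Amendment 11 the follow-up assessment list stops when safety follow-up ends, so the same rule now governs visits inside the window. A site that works visit by visit from 6.6 or the schedule is told not to collect SAEs it judges unrelated, in a period when 7.5.1.3 tells it to collect all of them.

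Type, incidence, seriousness and relatedness of AEs are primary safety endpoints. If the visit-level rule were followed, the SAE count after the EOT visit would be incomplete, and what entered it would depend on the investigator's causality call in an open-label combination. Section 5.3.5.1 warns that immune-related events can first appear months after the last pembrolizumab dose, so this is not a period to sample selectively.

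For LV-only patients the issue is different. Follow-up stops well before the SAE window does.

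**Working it through.** The plan states no figure to reproduce. The check is a comparison of rules and calendar arithmetic. All days are counted from the last dose.

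**Inputs**
- EOT visit: Day 30 to 37, collecting all AEs; a scan is taken unless one was done in the previous 28 days (6.5).
- First follow-up visit: 6 weeks ±1 week (35 to 49 days) after the most recent scan. Later visits follow at the same spacing, or every 12 weeks ±1 week after one year on study (6.6).
- SAE window: to Day 90 (7.5.1.3, SAP 6.7.1).
- Safety follow-up: 30 days for LV, 90 days for pembrolizumab (6.6).

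**Where the filtered visits fall**
- Scan at EOT: first visit from 30 + 35 = Day 65 to 37 + 49 = Day 86; second from 65 + 35 = Day 100 to 86 + 49 = Day 135.
- Scan up to 28 days before EOT (earliest 30 − 28 = Day 2): first visit from 2 + 35 = Day 37 to 37 + 49 = Day 86; second from 37 + 35 = Day 72 to Day 135.
- With 12-week spacing the second visit comes no earlier than 37 + 77 = Day 114.

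With EOT on schedule, the first follow-up visit always comes before Day 90 and a second sometimes does.

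**Length of the exposed interval.** From EOT to Day 90 is 90 − 30 = 60 days or 90 − 37 = 53 days, and less if EOT is delayed.

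**LV-only patients.** Footnotes T and V end follow-up at Day 30, leaving 90 − 30 = 60 days of the SAE window. An EOT visit on Days 31 to 37 is the only scheduled contact that could fall in it. If 6.6 is instead read as two clocks, with pembrolizumab stopped x days before the last LV dose, follow-up ends on Day max(30, 90 − x) and the gap is min(60, x) days. That is 21 days if x is one 21-day cycle, and the full 60 days once x reaches 60.

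**Rules side by side, EOT to Day 90**
- All SAEs: 7.5.1.3 (window), 7.5.1.4 (24-hour report), 7.5.1.2 (CRF and SAE form), 6.7 and footnote b of Figures 1 and 2 (any SAE while in safety follow-up), SAP 6.7.1 (count).
- Related SAEs only: 6.6 follow-up list, Appendix A footnote K, Appendix C footnote I.
- Concomitant medication after Day 30: Section 5.5.2 records it for SAEs with no relatedness condition; 6.6 adds one.

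**The case against.** The strongest reply is that the controlling text already covers the point. Section 6.7, directly after 6.6, requires any SAE to be monitored for and reported during safety follow-up, and footnote b of both figures repeats it. Sections 7.5.1.2 and 7.5.1.4 require every SAE to be recorded and reported regardless of cause. The AE row of the schedules also gives the 90-day limit; the Appendix C cell reads in part "AEs) or 90 days (SAEs". Unrelated SAEs would be missed only if a site followed one list item and its footnote and overlooked several other sections.

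This largely stands. A reader might infer that an SAE first judged unrelated would never reach the sponsor; the documents do not support that, since reporting is required whatever the causality call. The AE row helps less than it seems to: the related-only footnote also appears attached to the 90-day cell. The table layout is unclear there and should be checked in the PDF.

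The opening of 6.6 and the synopsis still describe follow-up of non-progressors to consent withdrawal, new therapy, death or study closure. On that reading some filtered visits fall after Day 90, where the filter fits. The visits before Day 90 remain filtered on either reading.

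For LV-only patients, 7.5.1.3 still sets a 90-day window, and 6.6 allows longer follow-up if safety concerns warrant it. Neither creates a contact, and the 6.7 duty ends with safety follow-up.

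**Conclusion.** There is a real contradiction between the visit-level collection rule and the SAE reporting rule. It creates a risk that unrelated SAEs are under-collected from the EOT visit (Day 30 to 37, or later) to Day 90, about 53 to 60 days. It is not a plan that leaves those events out.

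The interval applies to patients who stop treatment without progression. A reader might extend it to everyone who received pembrolizumab, but after progression or new therapy 6.6 moves patients to survival contacts, where its AE item does not apply. Nor does exposure start strictly at Day 31, because the EOT visit collects all AEs.

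The LV-only mismatch is separate. Taking footnotes T and V as written, the 6.7 duty covers none of Days 31 to 90 and no contact is scheduled after EOT, although 7.5.1.3 and the SAP count SAEs over that time.

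The documents give neither the number of SAEs affected nor the number of LV-only patients. A lower SAE count and a higher related share would follow only if sites applied the filter, and neither can be sized.

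**What to change.** 1. Reword the AE item in 6.6, Appendix A footnote K and Appendix C footnote I: all SAEs collected regardless of relationship through the 7.5.1.3 window, and only treatment-related SAEs after it. Bring the concomitant-medication part of the 6.6 item into line with 5.5.2.
2. Reconcile the LV-only end of safety follow-up (6.6, footnotes T and V, 4.4.2) with the 90-day SAE window in 7.5.1.3 and SAP 6.7.1. One low-cost option is a telephone SAE contact at Day 90. This would be a new contact: 6.6 provides for telephone contact only in survival follow-up.

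The cost is wording in two protocol sections and four footnotes, plus one call per LV-only patient if that option is taken. No endpoint or SAP analysis changes, since 7.5.1.3 and SAP 6.7.1 already assume these data.
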